- h. Pharmacokinetic (PK) plasma samples will be collected on Day 1 at time 0 (pre-dose; before the first dose on Day 1) and 24 hours after Dose 1. For TID dosing, samples will be obtained before Dose 7 and 0.5, 1, 2, 4, and 6 hours after Dose 7. This serial PK sampling for TID dosing may be done for Dose 7, 8, or 9, based on site/patient convenience. For BID dosing, samples will be obtained before Dose 5 and 0.5, 1, 2, 4, 6, and 8 hours after Dose 5. This serial PK sampling for BID dosing may be done for Dose 5, 6, or 7, based on site/patient convenience. For blood samples, a ± 10-minute window for time points ≤4 hours; ± 15 minute for time points between 4 and 24 hours. PK samples will also be obtained at any early study discontinuation visits. The timing of these PK samples relative to the last 2 (most recent) doses will be recorded. See [Section 3.1.4](#).
- i. Subjects can begin treatment with study drug before the DENV-serotype results are obtained.

- 
- j. Measurement of plasma viremia by viral titre and using a serotype-specific, real-time reverse transcription polymerase chain reaction (RT-PCR) assay. Subjects can begin treatment before the viral load results are obtained. See [Section 3.1.4](#) for details about the timing of this assay.
- k. Adverse events are collected beginning at screening. Treatment-emergent adverse events and serious adverse events will be assessed from the time of study drug dosing until end of study and should be followed until they are resolved, stable, or judged by the investigator to be not clinically significant.
- l. After subjects are confirmed eligible at screening, randomization and the initial dosing should occur within 24 hours, the initial dose should be given on the same day as screening, if possible. TID dosing at screening/Day 1 can begin in the morning, at mid-day, or in the evening (see [Section 3.1.2](#). BID dosing on Screening/Day 1 can begin in the morning or the evening (See [Section 3.1.3](#)).  
Note that if the initial dose of study drug is administered on the same day as screening (at mid-day or in the evening), the last dose(s) of study drug will be administered on Day 6.
- 

### 3.1.1 Screening/Day 1

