##### 4.1 INCLUSION CRITERIA

A patient must meet the following criteria to be eligible for participation in this study:

1. 18-55 years of age at time of screening
2. Fever  $\geq 38^{\circ}\text{C}$  (or feeling feverish) with onset during the previous 60 hours
3. Positive test confirming DENV on a NS1 antigen test or RT-PCR assay
4. Negative rapid diagnostic test results for SARS-CoV-2 and Influenza A and B
5. Body mass index (BMI) of 18 to 30  $\text{kg/m}^2$

6. Provides written informed consent prior to initiation of any study procedures
7. Able to understand and agrees to comply with planned study procedures and be available for all study visits
8. Males and females of childbearing potential must agree to use protocol-specified methods of contraception as described in [Section 4.1.1](#)
9. Male subjects must agree to not donate sperm from the first dose through 90 days after the last dose of study drug

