## 8.2 ANALYSIS SETS

The analysis populations are as follows:

- The primary analysis population is the modified intent-to-treat (mITT) population, which will include all randomized subjects who received at least 1 dose of study drug and have baseline and at least 1 post-baseline virology measurement. The primary analysis will also be performed on the per-protocol population of patients who completed treatment without a major protocol deviation.

- The PK population will include subjects who receive at least 1 dose of the study drug and have sufficient concentration data to support accurate estimation of at least 1 PK parameter.
- The safety population will include all subjects who receive at least 1 dose of study drug.
- A per protocol population will include the subset of the modified intent-to-treat population who completed study drug treatment without a major protocol violation.

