### 3.2.3 Exploratory Endpoints

Exploratory endpoints corresponding to exploratory objectives are:

Exploratory objective	Exploratory endpoints

PD	
 
• Change in DENV viral load (as measured by infectious viral titre) from baseline
 
• Area under the log 10-transformed viral load curve (AUC) from first dose to the end of treatment or study [as measured by DENV RNA and viral titre]
 
• Time to viral load clearance, which is defined as the first of 2 consecutive undetectable viral load measurements [as measured by DENV RNA and viral titre]
 
• Time to clearance of NS1 protein using a NS1 antigen test. Clearance is defined as time from start of treatment until the first of 2 consecutive plasma samples are NS1-negative.
 
• Subgroup analysis by DENV serotype: Change of DENV viral load [as measured by DENV RNA and viral titre] from baseline, viral load AUC, time to viral load, or NS1 clearance by DENV serotype
 
• Treatment-emergent amino acid substitutions in DENV NS5 polymerase
 
• Time to resolution or duration of fever
 
• Exploratory biomarkers on immunological response to dengue (See list in Section 12)
 
• Exploratory analysis to evaluate exposure-response relationship. The relationship between the exposure of AT-752 (and its metabolites) and DENV viral load measurement may be explored using graphic displays.
 

----	--

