#### **4.3. Analysis Population**

Primary endpoint analyses will be applied to the modified intent-to-treat population (mITT), which is defined as all randomized subjects who received at least 1 dose (full dose, unless assigned to placebo) of study drug (AT-752 or matching placebo) and have baseline and at least one post-baseline virology measurement. Change from baseline viral load (DENV RNA) will be compared between each AT-752 arm and a combined placebo group.

As-treated population is defined as all subjects who received at least 1 dose (full dose, unless assigned to placebo) of study drug (AT-752 or matching placebo) based on the actual treatment the patients received and had baseline and at least one post-baseline virology measurement.

The safety population will include all subjects who receive at least 1 dose of study drug.

The PK population will include all subjects who receive at least 1 dose of AT-752 and have sufficient concentration data to support accurate estimation of at least 1 PK parameter. PK parameter summaries will include only subjects in the PK population who have sufficient concentration measurement data to support estimation of the parameter. All subjects excluded from the PK population will be documented in the data listings.

The PD population will be the mITT population, which includes subjects who received at least 1 dose (full dose, unless assigned to placebo) of study drug and have baseline and at least 1 post-baseline viral load measurement.

The Per Protocol (PP) population will include the subset of the modified intent-to-treat population who completed study drug treatment without a major protocol violation that impact patient safety or data quality.

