Intermediate missing log 10-transformed viral loads (between baseline and the last day) will be linearly interpolated using the last and next available viral loads for AUC calculation for both AUCD5 and AUCD28. Subjects with intermediate missing values will be included in AUC analysis.

Time to viral load (as measured by DENV RNA and viral titre) or NS1 clearance, defined as time to first of 2 consecutive results of undetectable viral load or NS1, will be described using Kaplan-Meier methods. The median time to viral clearance and the estimated proportions of patients with viral clearance will be summarized by treatment group. Patients who do not receive a record of a negative test result by RT-PCR/viral titre or NS1 antigen assay by the last observation timepoint will be treated as censored at the final scheduled evaluation time point.

Subgroup analysis by DENV serotype will be carried out for the following endpoints: change of DENV viral load (as measured by DENV RNA and viral titre) from baseline, viral load AUC, time to viral load or NS1 clearance. Descriptive statistics (N, mean, standard deviation, median, minimum and maximum, and 95% CI) will be presented by treatment group.

Number and percentage of subjects with treatment-emergent amino acid substitutions in DENV NS5 gene will be compared between the treatment groups (chi-squared test).

Duration of fever is the sum of fever episode durations where fever episode duration is defined as the time from first fever measurement (either at baseline or following a period without fever) to the next measurement without fever. If the last episode has not resolved, duration for that episode will be

censored at the time of the last temperature measurement. Treatments will be compared by log-rank test.

Exploratory biomarkers may include plasma concentrations of cytokines (for example, TNF- $\alpha$ , IFN- $\gamma$ , IL-2, IL-4, IL-5, IL-6, IL-10, IL-12, IL-13, IL-1 $\beta$ , IP-10 and MCP-1). Data will be presented in descriptive statistics by treatment.

Exploratory analyses may be performed to evaluate exposure-response relationship. The relationship between the exposure of AT-752 (AT-281 and its metabolites AT-551, AT-229, and AT-273) and DENV viral load may be explored using graphical displays. Scatter plots of drug exposure versus change in DENC viral load will be provided.

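### Neither the mITT/PD population nor the clearance endpoints require a positive baseline, so patients with unquantifiable RNA dilute the primary effect on average, and patients already negative on an assay count as cleared

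*SAP*

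**What the plan says.** Entry: Protocol 4.1, criterion 3, accepts a "Positive test confirming DENV on a NS1 antigen test or RT-PCR assay", so either test is enough. Criterion 2 requires fever "with onset during the previous 60 hours".

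Dosing: the viral load sample is taken before the first dose, but footnote j of Protocol Table 3-1 says "Subjects can begin treatment before the viral load results are obtained".

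Primary population: SAP 4.3 defines mITT as randomised, dosed patients who "have baseline and at least one post-baseline virology measurement". Protocol 8.2 has the same condition ("have baseline and at least 1 post-baseline virology measurement"). SAP 4.3 adds that "The PD population will be the mITT population". The as-treated set has the same virology condition, and the per-protocol set is a subset of mITT. None of them asks for a detectable or quantifiable baseline.

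Model: SAP 8.1.1 sets values below LLOQ to half the LLOQ. It includes baseline viral load as a covariate but has no baseline-by-treatment term.

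Clearance: SAP 12 describes time to clearance of RNA, titre or NS1 by Kaplan-Meier, "defined as time to first of 2 consecutive results of undetectable viral load or NS1". SAP 3.2.3 says of NS1: "Clearance is defined as time from start of treatment until the first of 2 consecutive plasma samples are NS1-negative". Protocol 8.3.4 uses the same rule. No text covers a patient who is already negative at baseline.

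Replacement (Protocol 4.3.3, SAP 4.1) is triggered only by withdrawal without post-baseline virology. Evaluable virology data is not defined.

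**The concern.** The primary objective is reduction of DENV RNA. A patient who enters on NS1 with RNA below LLOQ starts at half the LLOQ, where no reduction can be recorded in any arm. Including such patients averages a zero effect into the comparison. The trial is meant to guide dose selection, and SAP 4.1 suggests reading an observed difference of 0.5 log10 as a possible signal, so the size of the estimate matters here more than the p-value.

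The clearance endpoints have a plainer problem. RNA, infectious titre and NS1 are three separate assays. Entry guarantees a positive result on only one of NS1 or RT-PCR, and never on titre. A patient who enters on RT-PCR and is NS1-negative before dosing, or whose titre is undetectable before dosing, meets the written definition at the first post-dose samples whatever the treatment.

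**Working it through.** **1. The plan's own power.** Inputs from SAP 4.1: effect 1 log10, SD 1.25, one-sided 0.10. Standard error = SD × √(1/n1 + 1/n2).

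- 15 vs 15: 1.25 × √(2/15) = 0.456. Noncentral t power is 0.81 (plan: 80%).
- 15 vs 5: 1.25 × √(1/15 + 1/5) = 0.645. Power is 0.59 (plan: 59%).

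Both reproduce. They assume that every patient can show the effect.

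**2. First-order dilution.** Let f be the share with baseline RNA below LLOQ. The documents do not give f, so the values below are assumptions. Expected difference = (1 − f) × 1 log10. SD is held at 1.25. The restricted column keeps the 1 log10 effect with 15 × (1 − f) per group and no replacement.

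| f | Expected difference, current mITT | Power, current mITT | Power, restricted set |
|---|---|---|---|
| 5% | 0.95 | 0.78 | 0.79 |
| 10% | 0.90 | 0.75 | 0.78 |
| 20% | 0.80 | 0.67 | 0.74 |

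**3. Simulation closer to SAP 8.1.1.** One time point, ANCOVA on baseline, 15 vs 15, true effect 1.0, residual SD 1.25. Assumptions not in the documents: baseline normal with mean 7 and SD 1.3 log10; LLOQ 3 log10, so that half the LLOQ is 3 − 0.3 = 2.7; baseline-BLQ patients stay at 2.7; placebo decline 2 log10.

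| f | Estimate, current mITT | Estimate, restricted set | Power, current | Power, restricted |
|---|---|---|---|---|
| 10% | 0.77 | 0.85 | 0.70 | 0.73 |
| 20% | 0.68 | 0.85 | 0.66 | 0.69 |

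The proportional rule holds: 0.85 × 0.9 = 0.77 and 0.85 × 0.8 = 0.68. Across repeat runs, with placebo declines of 1 and 2 log10, restriction gained about 1 to 4 points of power. That is less than the 7 points (0.74 − 0.67) in step 2 at 20%, because step 2 holds the SD fixed. Here the covariate absorbs these patients' different mean and their near-constant change lowers the residual variance, while restriction still loses patients.

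The restricted estimate is 0.85 and not 1.0 because post-baseline values are floored at the LLOQ. Restricting the population does not change that.

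**4. Chance imbalance.** With 15 per group and independent binomial counts, the probability that two groups differ by 2 or more such patients is 0.35 at f = 10% and 0.49 at f = 20%. The direction matters. With 3 baseline-BLQ patients on placebo and none on active (placebo decline 2 log10), the adjusted estimate is about 0.95, against 0.84 in the restricted set. The bias is then away from zero.

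**5. Clearance.** If a share f is already negative on an assay, each Kaplan-Meier curve has a step of about f at the first post-dose sample (about 24 hours, confirmed by the 48-hour sample), whatever the treatment. With 15 per group that is 1.5 patients expected at 10% (15 × 0.10) and 3 at 20% (15 × 0.20). The share may differ between RNA, titre and NS1, so one common baseline condition would not be enough.

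**The case against.** The size rests on a share that the documents do not give. Fever onset within 60 hours, a positive dengue test and the exclusion of illness suspected to come from another pathogen all point to few RNA-negative entrants. Under the baseline distribution assumed in step 3, almost no patient would fall below LLOQ naturally; the 10% and 20% are added on top. This stands, and the figures are a range and not a forecast.

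The analyses are declared descriptive (SAP 4) and are to be read with the totality of the data (SAP 4.1). SAP 8.1.2 plans the proportion above LLOQ, individual profiles and listings with BLQ marked, so these patients would be visible. Clearance is exploratory, with no between-arm test specified. That lowers the stakes, but no restricted analysis is prespecified and no clearance rule covers these patients. The baseline covariate does not restore the average effect, because there is no treatment-by-baseline term.

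Full mITT also answers a legitimate question: what happens in patients treated before their viral load is known. Hence a prespecified sensitivity analysis would be an acceptable minimum.

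Four stronger readings are tempting and are not supported:

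- That every dose-placebo difference is pulled toward zero, the more so under imbalance. Step 4 shows the opposite when the excess is on placebo.
- That power falls from 80% to 78%, 75% or 67% and the fix recovers it. The fix also removes patients, so the fair comparison is current against restricted.
- That these patients carry no information. RNA could rise after a BLQ baseline, and a drug could blunt that rise.
- That entry on NS1 is an eligibility error. It is a permitted confirmation.

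**Conclusion.** The gap is in the text of both documents and no section closes it.

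For the primary endpoint, the current mITT dilutes the estimated effect on average, roughly by the share of patients below LLOQ at baseline. Under the assumptions of step 3 this is 0.77 log10 at 10% and 0.68 at 20%, against 0.85 in the restricted set, a loss of 0.08 to 0.17 log10. If the true share is near zero, so is the loss. In any single comparison chance imbalance can push the estimate either way. The gain from restriction is mainly an undistorted estimate; the power gain is about 1 to 4 points.

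For clearance, the rule as written gives a wrong result for any patient already negative on the assay. The SAP does not say in words that such patients are events. It follows from a definition that requires no earlier positive and from the absence of any exception. This half does not depend on false-positive entrants or on the simulation.

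**What to change.** 1. SAP 12 and Protocol 8.3.4: restrict each time-to-clearance analysis to patients positive at baseline on that assay, separately for RNA, titre and NS1.
2. SAP 4.3 and 8 and Protocol 8.2: before unblinding, prespecify the change-from-baseline RNA analysis in mITT patients with pre-dose RNA at or above LLOQ. Preferably make it primary, with the current mITT as sensitivity analysis; at the least, make it a prespecified sensitivity analysis.
3. Report the number below LLOQ at baseline by arm.
4. Reconcile the BLQ rules, which affect these patients directly: half the LLOQ in SAP 8.1.1 and 10, but zero in the log10 summaries of SAP 8.1.2.

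The restriction uses a pre-dose sample, so it preserves the randomised comparison. The cost is document wording and a slightly smaller N: with no replacement, 13.5 per group on average at 10% (15 × 0.90) and 12 at 20% (15 × 0.80). The safety population is unchanged.

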### **5. Subject Disposition**

#### **5.1 Disposition**

The following will be summarized for the full analysis set, by treatment and overall for all subjects:

- The number of subjects who completed the study drug per protocol
- The number of subjects who completed the study
- The number of subjects who did not complete the study and study drug treatment (both overall and according to reasons for discontinuation from the study and study drug treatment)
- The number of subjects in each analysis population.

Subject disposition data will be presented in a data listing.

## **5.2 Protocol Deviations**

A protocol deviation is any change, divergence, or departure from the study design or procedures defined in the protocol. An important deviation (sometimes referred to as a major or significant deviation) is a subset of protocol deviations that leads to a subject being discontinued from the study, or significantly affects the subject's rights, safety, or well-being and/or the completeness, accuracy, and reliability of the study data. An important deviation can include nonadherence to inclusion or exclusion criteria or nonadherence to Food and Drug Administration (FDA) regulations or International Council for Harmonization (ICH) E6(R2) guidelines. Important protocol deviations will be summarized by treatment for all randomized subjects. All protocol deviations will be presented in a data listing, including the categorization of the deviation as important or not.

## **5.3 Inclusion and Exclusion Criteria**

Inclusion and exclusion criteria deviations will be presented in a separate data listing.

# **6. Demographics and Baseline Characteristics**

## **6.1 Demographics**

Demographic information collected at screening will be presented in a data listing.

Descriptive statistics will be calculated for the following continuous demographic characteristics:

- Age (years)
- Weight (kg)
- Height (cm)
- Body mass index (BMI) (kg/m^2)

Frequency counts and percentages will be tabulated for the categorical variables:

- Sex
- Race
- Ethnicity

The summaries will be presented by treatment and overall for the safety population.

## **6.2 Medical History**

The medical history data will be coded using the Medical Dictionary for Regulatory Activities (MedDRA version 24.1 or up) and presented in a data listing.

# **7. Treatments and Medications**

## **7.1 Prior and Concomitant Medications**

Medications that stop prior to the first dose of study drug will be classified as prior medication. Medications that start on or after the first dose of study drug will be classified as concomitant. If a

medication starts before the first dose of study drug and stops on or after the first dose of study drug, then the medication will be classified as both prior and concomitant.

All prior and concomitant medications will be coded according to the World Health Organization Drug Dictionary (version to be delineated in the CSR) and presented in a data listing.

## **7.2 Medical or Surgical Treatment Procedures**

Medical or surgical treatment procedures will be presented in a data listing.

## **7.3 Study Treatment**

Per the protocol, subjects are to receive study drug (AT-752 or matching placebo) orally either BID or TID for 5 days. Study treatment exposure (treatment duration and total dose received) will be summarized with descriptive statistics. A listing of patients, detailing dosing of study drug (including the timing of study drug administration) will be presented.

The duration of treatment exposure will be summarized with descriptive statistics for the safety population. The duration of treatment exposure [days] is defined as  $\{(last\ dose\ date)-(first\ dose\ date)\}+1$ . The total dose received will be summarized by the percentage of dose received relative to expected dose (per the protocol), where the unit for dose here will be the number of tablets. Study drug is administered as 250 mg tablets, so the expected number of tablets received is 45 tablets for 750 mg TID regimen, 40 tablets for the 1000 mg BID regimen, 60 tablets for the 1000 TID regimen, and 60 tablets for the 1500 mg BID regimen.

## **8. Efficacy**

Primary efficacy endpoint analyses will be applied to the modified intent-to-treat population, which is defined as all randomized subjects who received at least 1 dose of study drug and have baseline and at least one post-baseline virology measurement. The primary analysis will also be performed on the per-protocol population of patients who completed treatment without a major protocol deviation.

### **8.1 Primary Efficacy**

#### **8.1.1 Primary Endpoint**

The primary objective of this study is to evaluate the antiviral activity of AT-752 compared with placebo on change from baseline in DENV viral load (DENV RNA as measured by RT-qPCR) based on the log-10 scale at specified time points:

$$y_i = v_i - v_0$$

where  $v_i$  is the log10 DENV viral load measured at timepoint  $t_i$  and  $v_0$  is the log10 DENV viral load measured at baseline. Viral load measurements that are below the lower limit of quantification (LLOQ) will be set to  $0.5 \times \text{LLOQ}$  in the analysis.

Change from baseline in DENV viral load ( $y_i$ ) will be analyzed with repeated measures mixed model using the method of restricted maximum likelihood (REML). The model will include baseline viral load, treatment, time, and treatment-by-time interaction as fixed factors. An unstructured covariance matrix will be specified for the repeated statement. In case a mixed model with unstructured (UN) covariance matrix fails to converge, a compound symmetry (CS) structure will be used as an alternative. If neither of these converges, independent (ID) structure will be used. If none of these converges, the change from baseline by scheduled time point (ANOVA, Kruskal-Wallis) analysis will be presented as the primary analysis. The treatment group least squares mean (LSM) estimates for mean change from baseline and treatment group differences at each time point, with 80% CI, 95% CI and p-value will be presented.

